6.4 INVESTIGATIONAL PRODUCT ADMINISTRATION

Guidelines for dose preparation can be found in the pharmacy manual.

PRO 140 will be provided to the administering personnel in single-use syringes prepared from vials of study drug stored at 2-8°C at the site pharmacy prior to use. Each of two syringes is filled to deliver 1.0 mL or 2.0 mL of study drug for the 350 mg or 700mg dose, respectively

Equivalent volumes of study drug will be administered subcutaneously on opposite sides of the abdomen. However, based on subject preference or investigator discretion subjects receiving each of the doses can be administered using an alternate approach as follows:

350 mg Dose:

- One 2.0 mL injection on one side of the abdomen

700 mg Dose:

- Four 1.0 mL injections, on opposite sides of the abdomen, or other location

Note: *Patients with low body fat percentages may find subcutaneous injections uncomfortable especially in case of 2mL injection for the 700mg dosing. In such cases, PRO 140 700 mg can be injected as four 175mg/ml injections and/or subcutaneous injections can be placed at different areas other than abdomen as per discretion of the Investigator.*

A 25-gauge needle should be used to remove IP from vial and for administration to subjects.

IP should be administered slowly over 15 seconds per mL. IP should not be kept in syringe for more than 60 minutes.

Following each SC delivery of drug, careful examination will be made to assess the appearance of any study drug Injection Site Reactions (ISRs) as described in [Section 17.3](#).

All doses of study drug will be prepared by the credentialed pharmacist and will be administered as SC injection by a qualified medical professional (MD, DO, PA, LPN, LVN, NP, RN, or CMA if permitted by state law) or subject trained to self-administer study treatment.

Prior to self-administration, PI and/or study coordinator will train subjects on IP administration technique. Subject must demonstrate ability to perform injection in presence of PI/study coordinator before being allowed to administer subsequent weekly dose of study treatment outside clinic.

Site will dispense study treatment and injection administration supplies (i.e., syringes, needles, alcohol pads, gauze, band-aids, sharps container, frozen cooler pack, etc), and instruct subjects to return used IP vials/injection kit at next clinic visit.

Note: It is preferred that the same injection site be used throughout the study. At the same time, it is not recommended to inject the study drug into areas where skin shows signs of a previous injection site reaction. It is advised to change the injection site if any previous injection site reaction remains unresolved.

6.5 INVESTIGATIONAL PRODUCT RECEIPT AND ACCOUNTABILITY

Study drug must be used in accordance with this protocol and only under the direction of the responsible investigator. The investigational site must maintain complete and accurate records showing receipt and disposition of all study drug, including master records listing the date of receipt, the number and nature of medication units received, and a dispensing record which

includes each quantity dispensed, identification of the staff member to whom dispensed, the date of dispensing, the intended study participant, and the identification of the preparer.

Note: Site has option to maintain IP accountability via WebView IP Management system.

All used and unused study kits will be retained by the investigational site until drug accountability can be confirmed by study CRA during the monitoring visits. Similarly, accurate record of vials dispensed and returned to the investigational site should be kept for subjects performing self-administration.

Instructions will be provided by Sponsor regarding final disposition of all study drug in compliance with applicable regulations.

6.6 INVESTIGATIONAL PRODUCT DISPOSITION

All drug supplies are to be used only for this protocol and not for any other purpose. The investigator must not destroy any drug labels or any partially used or unused drug supply. At the conclusion of the study and as appropriate during the course of the study, the investigator will return all used and unused drug containers and drug labels to the drug distributor as directed by the Sponsor. A copy of the completed drug disposition form will be sent to CytoDyn, Inc. or to its designee.

7 DESCRIPTION OF PROTOCOL ASSESSMENTS AND PROCEDURES

7.1 INFORMED CONSENT

Written informed consent will be obtained for this study by the Investigator or designee from all subjects before the performance of any protocol-specific procedure. This study will be conducted in accordance with the provisions of the Declaration of Helsinki.

In obtaining and documenting informed consent, the Investigator must comply with applicable regulatory requirements and must adhere to Good Clinical Practice (GCP). The Investigator, or designee, must fully inform subjects of all pertinent aspects of the study. Before informed consent may be obtained, the Investigator, or a person designated by the Investigator, must provide the subject ample time and opportunity to inquire about details of the study and to decide whether or not to participate in the trial. All questions about the trial must be answered to the satisfaction of the subject. Prior to the subject's participation in the trial, the written informed consent must be signed and personally dated by the subject and by the person who conducted the informed consent discussion. Authorization for release of protected health information must also be obtained, as per local policies.

7.2 ASSESSMENT OF ELIGIBILITY

During the Screening Phase and at TE1 Visit (prior to treatment administration), the Investigator must assess a subject's continued suitability and eligibility for the trial. The Inclusion and

Exclusion criteria of this Protocol are described in [Sections 3.3.1](#) and [3.3.2](#). If the subject is not suitable or eligible for the trial then the subject will be a screen failure.

7.3 DEMOGRAPHIC INFORMATION

For the purposes of this study, demographic information will include:

- Dates of ICF signature
- Date of birth
- Gender
- Race (American Indian/Alaskan Native, Asian, Black/African American, Native Hawaiian/Pacific Islander, Caucasian, or other)
- Ethnicity (Hispanic/Latino or Not Hispanic/Latino)
- Time Since HIV Diagnosis (yrs.)

7.4 MEDICAL HISTORY

Note: Medical history collected at the time of screening for PRO 140_CD 01 protocol will be carried forward. Medical history will not be collected for the PRO 140_CD 01-Extension protocol.

7.5 PRIOR / CONCOMITANT MEDICATIONS AND NON-STUDY TREATMENTS

A complete history of antiretroviral therapies will be recorded in the source documents and on the appropriate page of the eCRF.

In addition to this, all other medications and therapies administered or taken by the subject beginning 30 days prior to first Screening Visit and throughout the study will be recorded. Subjects must be questioned at each study visit concerning any new medications or changes in current medications including over-the-counter medication.

For each medication and non-study treatment, the following will be documented:

- Medication/treatment name (generic name may be used if trade name is unknown)
- Dose, unit, and frequency of dosing (individual dosages, not total daily dose).
 - **Note:** *Each new dose of medication should be recorded as a separate entry, with the exception of medications that are given on a sliding scale. For these, it is*

acceptable to enter the range of the dosage, including the start and stop dates for which the specified dosage range was used.

- Route of dosing
- Indication for use
- The start date
- The stop date (if medication/therapy is not ongoing)

Please refer to Exclusion Criteria ([Section 3.3.2](#)) for a list of prohibited treatments and/or procedures. All other medications that are appropriate for the care of the subject may be prescribed. If concomitant medications are started during the study, the indication for the concomitant medication should be considered an AE.

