4.2 TREATMENT EXTENSION PHASE

Treatment Extension Phase begins with an evaluation of results of laboratory samples collected during the Screening Phase. Subjects who meet all eligibility criteria, as per data gathered from Screening Phase are to be treated. All subjects who fail to meet eligibility criteria will be considered screen failures, exit the study without further evaluation and enter the Follow-up Phase of the PRO 140_CD 01 Treatment Substitution protocol.

Eligible subjects will receive PRO 140 weekly SC treatments, given every week (\pm 3 days) or until virologic failure, whichever occurs first.

PRO 140 will be administered as a 350 mg subcutaneous injection weekly. The study treatment (PRO 140 SC injections) will be administered by a qualified medical professional (MD, DO, PA, LPN, LVN, NP, RN, or CMA if permitted by state law) or subjects trained to perform self-administration of study treatment (see [section 6.4](#)).

Note: Patients enrolled under a previous Protocol (V.1.0-9.0) have the option of increasing their dose to receive 700mg weekly for the remainder of the Treatment Extension Phase.

All study subjects will re-initiate their previous antiretroviral regimen:

- One week prior to the end of Treatment Extension Phase, or
- Anytime during the Treatment Extension Phase, if virologic failure occurs or have met any other criteria for discontinuation of study treatment as specified in [section 5.2.1](#) of the protocol.

Note:

- In case of increase in plasma HIV-1 RNA levels above 200 copies/mL, subjects will return to clinic for another blood draw in-between the Treatment Visits for repeat plasma HIV-1 RNA levels, as per the discretion of the Investigator.
- Subjects who experience virologic failure (defined as two consecutive HIV-1 RNA levels of \geq 400 copies/ml separated by at least 3 days) at any time during the Treatment Extension Phase will undergo the Virologic Failure (VF) Visit assessments and enter the Follow-up Phase of the study.
- Subjects who meet any criteria (other than virologic failure) for discontinuation of study treatment as specified in [section 5.2.1](#) of the protocol, will undergo TE161 Visit assessments and enter the Follow-up Phase of the study.
- Subjects who do not experience virologic failure will enter the Follow-up Phase of the study at the end of 161-week Treatment Extension Phase.

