7.5.1 Excluded Medications and Therapies

1. Use of concomitant antiretroviral therapy is NOT allowed during the Treatment Extension Phase of the study EXCEPT for one week overlap of oral retroviral regimen and PRO 140 at the end of the treatment in subjects who do not experience virologic failure. Subject is allowed to re-initiate their previous antiretroviral regimen during the Treatment Extension Phase, if virologic failure occurs or if subject meets any other criteria for discontinuation of study treatment as specified in [section 5.2.1](#) of the protocol.
2. Use of oral or parenteral corticosteroids (>5 mg/day) is NOT allowed during the study, with the following exceptions:
 - Use of chronic systemic corticosteroids at replacement doses (e.g., < 5mg/day prednisone) AND use of inhaled, nasal, or topical steroids are allowed.
3. Use of radiation or cytotoxic chemotherapy, immunosuppressants and immunomodulating agents (e.g., interleukins, interferons) or agents with known anti-HIV activity (i.e., hydroxyurea, foscarnet) are NOT allowed during the study.

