8.7.5.1 Adverse Events

Adverse events will be coded using Medical Dictionary for Regulatory Activities (MedDRA). TEAEs are defined as events with an onset on or after the first treatment. TEAEs will be summarized by treatment group, System Organ Class, and preferred term. The following TEAE summaries will be provided:

- TEAEs by severity grade
- TEAEs by relationship to study treatment.

In addition, separate summaries of SAEs, and AEs resulting in discontinuation of study treatment will be presented.

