9.1 ADVERSE EVENT

An adverse event (AE) is defined as any unfavorable or unintended sign, symptom, or disease that occurs or is reported by the subject to have occurred, or a worsening of a pre-existing condition. An AE may or may not be related to the study treatment.

AEs will be elicited through direct questioning and subject reports. Any abnormalities in visit evaluations, physical examination findings or laboratory results that the Investigator believes are clinically significant to the research subject and that occurred after initiation of the first study treatment will be reported as AEs. Abnormal findings that are NOT clinically significant (NCS) should not be recorded as an AE.

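### The rule that makes the indication for any newly started medication an AE conflicts with the protocol's own AE definition, and TEAEs have no stated end, so events on restarted ART are pooled with events on PRO 140

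*Protocol*

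**What the plan says.** Protocol Section 7.5 closes its rules on recording medication with this: "If concomitant medications are started during the study, the indication for the concomitant medication should be considered an AE". No medication or reason for prescribing is exempted.

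Section 9.1 defines an AE as an unfavourable or unintended sign, symptom or disease, "or a worsening of a pre-existing condition".

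Section 4.2 states: "All study subjects will re-initiate their previous antiretroviral regimen". This happens one week before the end of the Treatment Extension Phase, or earlier at virologic failure or another reason for stopping. Section 7.5.1 places that therapy among concomitant treatments: "Use of concomitant antiretroviral therapy is NOT allowed during the Treatment Extension Phase of the study EXCEPT for one week overlap". Section 7.5, on the other hand, gives ART a record of its own ("A complete history of antiretroviral therapies will be recorded in the source documents") and then continues: "In addition to this, all other medications and therapies administered or taken by the subject".

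On timing, Section 8.7.5.1 says: "TEAEs are defined as events with an onset on or after the first treatment". It gives no end. Section 9.1.1 collects AEs up to the final study visit: NVF-EFU2 for subjects without failure, and viral suppression for subjects with failure. Table 4-9 shows the previous antiretroviral regimen in use at those follow-up visits. Section 8.2.3 lists the frequencies of Grade 3 or 4 AEs and of treatment-emergent SAEs as safety endpoints. Section 8.1 describes a single active arm.

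**The concern.** There are two separate problems.

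First, the rule in Section 7.5 and the definition in Section 9.1 give different answers for the same event. A medicine may be started for prevention, or because the protocol requires it, when nothing unfavourable has happened. Section 7.5 then records an AE and Section 9.1 does not. AE counts would depend partly on which section a site followed.

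Second, a TEAE definition with a start and no end pools two exposures: time on PRO 140, and time on restarted combination ART after PRO 140 has stopped. The secondary objective is the long-term safety and tolerability of continued PRO 140. With one arm there is no concurrent group against which a reader could separate the two. The treatment-emergent SAE frequency is counted regardless of relationship, so an SAE that begins weeks into restarted ART counts in it.

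**Working it through.** The protocol gives no figure that depends on either rule, so there is nothing to reproduce. The check is a cross-reading followed by simple arithmetic on time at risk.

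**1. The AE rule against the AE definition**

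| Situation | Section 7.5, literally | Section 9.1 |
|---|---|---|
| New drug for a new or worsened illness | AE | AE |
| New drug for prevention, nothing worsened | AE | Not an AE |
| Planned ART restart, HIV still suppressed | AE, if ART counts as concomitant (as in 7.5.1) | Not an AE |
| ART restart at virologic failure | AE, on the same condition | May be an AE, since rebound can be a worsening |

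The second row is a conflict whatever is decided about ART. The third depends on how Sections 7.5 and 7.5.1 are read together.

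**2. Share of the AE reporting window spent on ART, no virologic failure**

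Inputs: 161 weekly visits (Section 4.2 and Table 4-7), taken as 160 weeks from first to last dose; one week of overlap with ART; four weeks of follow-up (Section 4.3).

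- Reporting window: 160 + 4 = 164 weeks.
- Time on ART: 1 + 4 = 5 weeks.
- Share: 5/164 = 3.0%.

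The synopsis lets treatment run beyond this, which would make the share smaller.

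**3. The same share after virologic failure**

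Share = f/(v + f), where v is the week of failure and f the weeks on ART until re-suppression. The protocol sets no maximum for f. The values below are assumptions based on the four-weekly visits.

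| Failure at week v | f = 4 | f = 8 | f = 12 |
|---|---|---|---|
| 4 | 50% | 67% | 75% |
| 52 | 7% | 13% | 19% |
| 160 | 2% | 5% | 7% |

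**4. How much of follow-up lies beyond plausible PRO 140 effect**

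Section 1.5.2.4 gives a mean serum half-life of 3.5 to 3.9 days after single IV doses. Five half-lives are 5 × 3.5 = 17.5 to 5 × 3.9 = 19.5 days. Section 1.5.2.5 reports receptor occupancy above 85% for 29 days after single IV doses. Neither is a figure for repeated SC dosing, so both are only guides.

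- Four weeks (28 days): 28 − 19.5 = 8.5 to 28 − 17.5 = 10.5 days lie beyond five half-lives. None lie beyond 29 days.
- Twelve weeks (84 days): 84 − 19.5 = 64.5 to 84 − 17.5 = 66.5 days lie beyond five half-lives, and 84 − 29 = 55 days beyond the occupancy period.

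**The case against.** **ART is recorded apart from other medication.** Section 7.5 separates ART history from the general log, and the schedules give ART and concomitant medications separate rows. A reader might infer that the restart becomes an AE in every subject. The documents do not support that. It would need one recording rule to override both this separation and Section 9.1; it ignores subjects with no recorded restart; and rebound at failure may be a genuine AE. What stands is that the text is ambiguous for ART and in conflict for other medicines started without a new or worsened condition.

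**AE collection does end.** Section 9.1.1 stops it at the final study visit, so TEAE status is not unlimited. Section 4.3.1 might suggest AE collection at the 12- and 24-month visits after failure, but Section 9.1.1 stops at viral suppression and Table 4-9(c) has no AE row. It is also fair that an on-treatment cut-off is often set in the SAP, which is not at hand. However, Section 8.7.5.1 does not leave the definition open; it states one.

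**Treatment-emergent does not mean related.** Section 9.1.4 requires a causality category for every AE, and Section 8.7.5.1 tabulates TEAEs by relationship. The plan therefore does not attribute ART-period events to PRO 140. Onset dates are recorded, so late events can be identified. This objection stands, though the treatment-emergent SAE endpoint itself is not restricted to related events.

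**The size is easily exaggerated.** One could set 100% any-AE incidence under the literal rule against 29/43 (67%) in CD 01. That comparison fails. CD 01 had 14 weeks of treatment (Table 1-1); at a constant hazard, an assumption, any-AE incidence by week 52 would already be 1 − (14/43)^(52/14) ≈ 98%. Any-AE incidence is also not a listed safety endpoint, and a planned restart does not by itself enter the Grade 3 or 4 or SAE counts.

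**Counting follow-up events is cautious.** For subjects without failure, four weeks lie within the 29-day occupancy period, so counting those events as emergent is defensible. That reasoning does not extend to long follow-up on ART after failure.

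**Conclusion.** The point holds in a limited form. The Section 7.5 rule is broader than the Section 9.1 definition and, as written, the two can produce different AE counts from the same facts. The TEAE definition pools on-PRO 140 time with later ART-only time, and this reaches the treatment-emergent SAE frequency.

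The pooling matters little for subjects without failure. It can matter for subjects who fail early, where half or more of the reporting window may be ART time under the assumed timings. Failure is not rare in this programme: Section 1.5.2.7 reports that 23 of 43 subjects (54% as stated there) completed 12 weeks without it, although only such completers may enter this extension.

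Safety is descriptive, with at most 28 subjects planned, so no test or decision rule is affected. The consequence is for how the safety tables can be read. If the SAP already separates the two periods, only the protocol sentence on TEAEs needs aligning, and the conflict between Sections 7.5 and 9.1 remains.

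**What to change.** In Section 7.5, replace the last sentence with one that refers to Section 9.1: a newly started medication prompts an AE only when its indication is itself a new or worsened condition. Add that a planned, protocol-required restart of ART is not in itself an AE, while rebound at virologic failure is judged under Section 9.1.

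In Section 8.7.5.1, keep every event, but tabulate TEAEs, Grade 3 or 4 AEs and SAEs separately for two periods: on PRO 140, up to a time after the last dose fixed in advance with its pharmacological basis stated, and the later period on ART alone. By-subject listings should continue to cover the whole study.

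The cost is two amended passages and one extra table. The downside is that some late events appear in a second table, where they remain visible.

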7.5.1 Excluded Medications and Therapies

1. Use of concomitant antiretroviral therapy is NOT allowed during the Treatment Extension Phase of the study EXCEPT for one week overlap of oral retroviral regimen and PRO 140 at the end of the treatment in subjects who do not experience virologic failure. Subject is allowed to re-initiate their previous antiretroviral regimen during the Treatment Extension Phase, if virologic failure occurs or if subject meets any other criteria for discontinuation of study treatment as specified in [section 5.2.1](#) of the protocol.
2. Use of oral or parenteral corticosteroids (>5 mg/day) is NOT allowed during the study, with the following exceptions:
 - Use of chronic systemic corticosteroids at replacement doses (e.g., < 5mg/day prednisone) AND use of inhaled, nasal, or topical steroids are allowed.
3. Use of radiation or cytotoxic chemotherapy, immunosuppressants and immunomodulating agents (e.g., interleukins, interferons) or agents with known anti-HIV activity (i.e., hydroxyurea, foscarnet) are NOT allowed during the study.

7.5.2 Allowable Medications and Therapies

All other medications/therapies that are not otherwise prohibited and, in the judgment of the Investigator, are required for proper medical care of the subject may be prescribed.

7.6 PHYSICAL EXAMINATION

The complete physical examination will include routine examinations for the following:

- Head, Ears, Eyes, Nose, Throat (HEENT)

- Abnormalities of the extremities
- Neurologic abnormalities
- Heart/cardiovascular abnormalities
- Musculoskeletal abnormalities
- Dermatologic abnormalities
- Any other body system for which an abnormality is noted and which, in the opinion of the Investigator, is relevant to the safety of the subject or could impact safety or efficacy results for the subject; i.e., the abnormality is clinically significant (CS).

Each abnormality will be recorded and the Investigator will record an assessment of its clinical significance.

The complete physical examination will be conducted at the first Screening Visit (SV1), End of Treatment (EOT) Visit, and at VF visit in case of virologic failure. Only symptom-directed physical examination will be performed at other Treatment Visits.

